1. SYNOPSIS

Study Title	Investigating non-invasive brain stimulation to enhance fluency in people who stutter
Internal ref. no. / short title	INSTEP Trial
Study Design	Double-blind randomised controlled trial. Active treatment: bi-hemispheric tDCS, Control: Sham tDCS. Minimisation randomisation.
Study Participants	Healthy adult males with developmental stuttering and healthy male controls with no speech disorders
Planned Sample Size	70 (40 participants with developmental stuttering, 30 control participants)
Planned Study Period	1 st November 2017 – 30th April 2020
	Outcome Measures
Primary	Change from baseline (i.e. baseline subtracted) in a clinical measure of stuttering severity (SSI-4), post training (1 week, 6 weeks, and 3 months after training).
Secondary	Change from baseline (i.e. baseline subtracted) in: (i) % disfluent syllables produced during conversation; (ii) % disfluent syllables produced during reading post training (1 week, 6 weeks, and 3 months after training). (iii) total score on an attitudinal measure (OASES), post training (6 weeks, and 3 months after training).
Other Pre-specified	Change from baseline (i.e. baseline subtracted) in: (i) total score on the Premonitory Awareness in Stuttering Scale; (ii) total score on the Beck Anxiety Inventory; (iii) subjective and objective ratings of stuttering severity and naturalness, post training (1 week, 6 weeks, and 3 months after training). Changes from baseline (i.e. baseline subtracted) % disfluent syllables produced during (i) conversation and (ii) reading, during the 5-day training (immediately post intervention days 1 to 5; immediately pre-intervention days 2 to 5).
	Exploratory (non-behavioural) measures
Other	We will use MRI and TMS, to evaluate neural structure, function, and excitability in people who stutter and in healthy controls. Using MRI, we will also obtain images of the vocal tract during speech. These measurements will be obtained just before training begins and 1 week after the end of the training in people who stutter and once only in healthy controls.

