9.2. The Number of Participants

We plan to recruit 40 PWS and up to 30 controls. The sample size was determined based on previous cross-sectional studies in stuttering, including our own. A sample size of 20 participants in each group is higher than most previous behavioural and functional imaging studies in PWS. This should ensure sufficient sensitivity to detect differences in behaviour, brain structure and function. It should also allow us to determine the relationship between the experimental variables and other measures such as stuttering severity and duration of stuttering. A sample size of 20 for each group should detect a group difference with an effect size of 0.9 at 80% power and 5% false positive rate. For the tDCS study across 5 days, we will compare two groups of 20 PWS. In our previous study, with sample sizes of 15 in each group, effect sizes of 0.93 and 0.50 were obtained for the reduction in the SSI at 1 week and 6 weeks post intervention.

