The primary outcome measure for the trial is the change in stuttering severity, measured using the Stuttering Severity Instrument, version 4 (SSI-4, Riley, 2009). Change from baseline score will be calculated (by subtraction of the baseline) at one week, 6 weeks and 12 weeks following the intervention. Change scores will be entered into a mixed model analysis of variance (ANOVA), with stimulation group (tDCS, sham) as the between subjects factor and speaking task and time point (1 week, 6 weeks, 12 weeks) as the within subjects factor. If a significant interaction between stimulation group and time point is found, separate repeated measures ANOVAs will be performed for each stimulation group or with three planned comparisons between groups at each time point.

Secondary outcome measures

We have three secondary outcome measures:

- i. Change from baseline score in percentage of disfluent syllables, during reading.
- ii. Change from baseline score in percentage of disfluent syllables, during conversation.
- iii. Change in total score on Overall Assessment of a Speaker's Experience of Stuttering (OASES).

Change in percentage of disfluent syllables will be calculated by subtraction of the baseline percentage for reading and conversation separately at one week, 6 weeks and 12 weeks following the intervention. Data will be analysed as described above for the primary outcome measure. Anticipating a significant effect of group in both measures, we will also compare the changes in reading with those in conversation at each time point separately for the tDCS group.

To test for the effects on the OASES measure, we will use a mixed model ANOVA with stimulation group (tDCS, sham) as the between subjects factor and time point (6 weeks, 12 weeks). We will not collect data at the 1-week post-intervention time-point to avoid violating test-retest validity of the scale. If a significant

interaction between stimulation group and time point is found, separate planned comparisons between groups will be performed for each time point.

Other pre-specified measures

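### Between-arm comparisons at each follow-up are pre-specified only if the group-by-time interaction is significant, so a steady benefit would usually have no planned estimate by visit

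*SAP*

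**What the plan says.** The synopsis sets the primary outcome, SSI-4 change from baseline, at three visits: "post training (1 week, 6 weeks, and 3 months after training". The SAP, under Primary outcome measure, repeats this: "Change from baseline score will be calculated (by subtraction of the baseline) at one week, 6 weeks and 12 weeks following the intervention". Its third visit, 12 weeks, is taken here as the protocol's 3-month visit.

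The planned model is a mixed ANOVA "with stimulation group (tDCS, sham) as the between subjects factor and speaking task and time point (1 week, 6 weeks, 12 weeks" within subjects. Visit-level analysis then depends on a condition, namely "If a significant interaction between stimulation group and time point is found". What the SAP provides for once that is satisfied is "separate repeated measures ANOVAs will be performed for each stimulation group or with three planned comparisons between groups at each time point". Even when the condition is met, the word 'or' allows within-arm analyses in place of between-arm ones.

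The condition spreads to other outcomes:

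- **Percentage of disfluent syllables:** "Data will be analysed as described above for the primary outcome measure".
- **OASES (6 and 12 weeks):** again only after a significant interaction, "separate planned comparisons between groups will be performed for each time point".
- **Anxiety, premonitory awareness, severity and naturalness ratings, and the SSI-4 submeasures:** the SAP refers each of these back to the primary analysis.

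Protocol sections 9.1 and 9.3 add no unconditional contrast. Section 9.1 says only that changes will be compared between groups with mixed designs. The one unconditional comparison by visit in the SAP, reading against conversation, is made within the tDCS arm alone.

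**The concern.** The interaction asks whether the treatment effect differs between visits. It does not ask whether there is an effect at any visit. Using it as the entry condition means that the visit-level contrasts are planned when the effect fades or grows, and not planned when it stays the same. The Background section of the protocol sets out to replicate a gain that lasted some weeks after training, so durability is the trial's own question.

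Two things are at stake. First, the difference at each visit, with its interval, is what a reader needs in order to judge whether a benefit is present at 3 months; an average over three visits does not answer that. Second, when the effect does wane, the estimates that pass the gate come from trials selected for a large spread between visits, which can push the 1-week estimate upward.

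**Working it through.** **Inputs from the documents.** 20 per arm (protocol section 4); detectable effect 0.9 at 80% power and a 5% false positive rate (section 9.2); earlier results in section 9.2, "effect sizes of 0.93 and 0.50 were obtained for the reduction in the SSI at 1 week and 6 weeks post intervention".

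**Assumptions.** Two-sided 5%; effects in SD units of the change score; equal variances; equal correlation ρ between visits, varied from 0.3 to 0.9; a 12-week effect of 0.30 or 0.50; complete data; normal parametric ANOVA; the speaking-task factor ignored. The documents supply neither ρ nor a 12-week effect.

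**Step 1: the plan's own figure.** A two-sample t test with 20 per arm and d = 0.9 has 79.2% power (81.2% by normal approximation). The stated 80% is reproduced.

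**Step 2: how often the gate opens.** The interaction F test has 2 and 76 degrees of freedom and noncentrality λ = (n/2) × Σ(d_t − d̄)² / (1 − ρ), with n/2 = 10.

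- Constant effect: every d_t equals d̄, so λ = 0 and the gate opens in 5% of trials at any ρ.
- (0.93, 0.50, 0.50): d̄ = 0.643 and the sum of squares is 0.123. At ρ = 0.5, λ = 10 × 0.123/0.5 = 2.47 and power is 26%.
- (0.93, 0.50, 0.30): d̄ = 0.577 and the sum of squares is 0.207. At ρ = 0.7, λ = 10 × 0.207/0.3 = 6.91 and power is 63%.

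| ρ | constant | 12-week effect 0.50 | 12-week effect 0.30 |
|---|---|---|---|
| 0.3 | 5% | 20% | 31% |
| 0.5 | 5% | 26% | 41% |
| 0.7 | 5% | 41% | 63% |
| 0.8 | 5% | 58% | 81% |
| 0.9 | 5% | 88% | 99% |

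For OASES (two visits, 1 and 38 degrees of freedom), equal effects again give 5%. Assumed effects of 0.5 then 0.2 give λ = 10 × 0.045/(1 − ρ), hence 15% at ρ = 0.5 and 31% at ρ = 0.8.

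**Step 3: the ungated group main effect.** The mean over three visits has SD √((1 + 2ρ)/3). For constant d = 0.9, the noncentrality is 0.9 × √10 divided by that SD. At ρ = 0.3 it is 2.846/0.730 = 3.90, power 97%. At ρ = 0.9 it is 2.846/0.966 = 2.95, power 82%.

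**Step 4: selection of the 1-week estimate (simulation).** With a true 1-week effect of 0.93 and ρ of 0.5–0.7, the mean 1-week difference among trials passing the gate runs from about 1.01 to 1.135. As ratios, 1.01/0.93 ≈ 1.08 and 1.135/0.93 ≈ 1.22, so it is about 8–22% too large. At ρ = 0.9 the excess is 0–2%. Under a constant effect there is no material excess.

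**Step 5: consequence of removing the gate.** Each visit contrast has a 95% CI half-width of 2.024 × √(2/20) = 0.64 SD. With no effect at any visit, three unadjusted tests give at least one false positive in about 9–13% of trials (ρ 0.9–0.5), against 1–2% through the gate.

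**The case against.** The best defence is that the group main effect sits in the same ANOVA and is not gated. If the benefit is constant, that average estimates the effect at every visit, and more precisely than any single visit. Its power of 82–97% exceeds the single-visit 79%. In the waning patterns at ρ of 0.5–0.7, either the main effect or the interaction is significant in about 75–82% of trials. This stands, and it rules out the stronger inference that a sustained benefit would be missed or go unreported. Nor does the SAP forbid descriptive means by visit; it simply plans no between-arm estimate there without the interaction.

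Four further limits also stand:

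- The 5% figure belongs to a flat effect. The protocol's own earlier pattern is not flat, and at high correlation the gate would usually open.
- A reader might take the section 9.2 power figure to describe the 1-week contrast. That sentence names no visit, and the 0.93 at 1 week appears separately as a result of the earlier study.
- Inflation of the 1-week estimate is not general (Step 4).
- The SAP says non-normal variables will be analysed nonparametrically, so the test actually used as the gate may differ from the one modelled.

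It might also be said that calling the comparisons planned implies that they will always be run. The sentence makes them depend on the interaction, so this does not rescue the text.

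What the defence cannot supply is the visit-level answer. An average over 1, 6 and 12 weeks does not show whether the benefit is present at 3 months, and a non-significant interaction at this sample size does not establish that the effect is constant.

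**Conclusion.** The concern holds in a limited form. The SAP pre-specifies no between-arm contrast or interval at any follow-up unless the group-by-time interaction is significant, for SSI-4, OASES and the measures that refer to the primary analysis. The gate opens in 5% of trials when the benefit is equal at all visits. For the earlier 0.93 and 0.50 with an assumed 12-week effect of 0.30–0.50, it opens in anything from about 20% to 99%, depending chiefly on a correlation that the documents do not give.

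The loss is of planned estimation by visit, not of the ability to detect a lasting benefit. The upward bias in the 1-week estimate (about 8–22%) applies to a waning effect with correlation 0.5–0.7 and largely disappears at 0.9. All figures assume complete data and a normal parametric ANOVA with 20 per arm. The plan should be changed, since the remedy uses the same model and data.

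**What to change.** In the SAP, under Primary outcome measure and Secondary outcome measures, delete the interaction condition for SSI-4 and OASES, and make clear that the deletion carries over to every measure analysed in the same way. Replace it with text to this effect: the overall tDCS-versus-sham effect from the mixed model is the confirmatory test; the tDCS-minus-sham difference with its 95% CI is reported at each follow-up (three for SSI-4, two for OASES) whatever the interaction result; the interaction is reported as supportive. Drop the alternative of separate within-arm ANOVAs as a substitute for the between-arm contrasts.

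Removing the gate also removes the control it gave over the visit-level tests. The SAP should therefore either label the visit contrasts as estimation only, or name a primary time point or a multiplicity rule such as Holm.

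The cost is wording, a few more estimates from the same data and one stated multiplicity choice. No extra participants, visits or measurements are needed. The intervals will be wide, at about ±0.64 SD per visit, and should be presented as such.

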9. STATISTICS AND ANALYSIS

9.1. Description of Statistical Methods

Behavioural data measuring the primary outcome (speech function) will be acquired before, during and after brain stimulation using audio and video recordings. Measures of speech fluency (e.g. Stuttering Severity Instrument score, % disfluency) will be taken from these recordings and will be subjected to standard statistical analyses using software such as SPSS. Mixed between- and within-subject designs will be used to compare changes in performance (baseline subtracted) on speech measures between the two groups of participants (tDCS vs. sham). The investigator team have prior experience in statistical analysis of similar behavioural data.

Brain imaging data (MRI) will be analysed using the FMRIB Software Library (FSL) which involve standard approaches for the analysis of functional imaging data. We will also be using novel approaches that allow us to explore functional connectivity, such as probabilistic Independent Component Analysis. The investigator team has substantial with MRI analysis using FSL and SPM.

Vocal Tract Images will be analysed using custom tools implemented in MATLAB.

TMS data will be analysed using custom tools and software to compare measures of cortical excitability within participants between hemispheres, and across time points, and between groups at the baseline timepoint.

While the study is ongoing, we will be able to compare brain and vocal tract imaging, and TMS data in PWS vs controls once we have data from the baseline timepoint. Unblinding is not required for these baseline analyses.

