Study Title: Investigating Non-invasive brain Stimulation To Enhance fluency in People who stutter

Short title: INSTEP Trial
University of Oxford, Medical Sciences Division
IDREC Ethics Ref: R52173/RE001

Document title: INSTEP trial statistical analysis plan
Date and Version No: 23rd October 2017, version 1.0

Chief Investigator: [name], Department of Experimental Psychology, University of Oxford

Investigators: [name], Department of Experimental Psychology, University of Oxford

[name], Department of Experimental Psychology, University of Oxford

[name], Department of Experimental Psychology, University of Oxford

All the investigators declare that there are no conflicts of interest associated with the proposed study.

INSTEP trial statistical analysis plan

We plan to carry out analyses on the 'intention to treat' sample, i.e. including all participants who complete the study. If any participant has data that are group outliers, we will also complete sensitivity analyses (Thabane et al., 2013) by re-running all analyses excluding the relevant participant(s), to evaluate the robustness of the treatment effect. Speech data in people who stutter tends to significantly deviate from a normal distribution. Transformation of these data is problematic for reporting confidence intervals in interpretable units, therefore we will use change scores (baseline subtracted) in the analyses to overcome this limitation. For consistency, we will use this approach of baseline subtraction and analysis of change scores in analysis of other variables even if they do not suffer from the same skewness as the speech data. Variables that are not normally distributed will be analysed using nonparametric methods.

Primary outcome measure

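### After a group-by-time interaction, the SSI-4 plan allows within-arm ANOVAs in place of tDCS-versus-sham comparisons, and its model lists a speaking-task factor for which no SSI-4 score is described

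*SAP*

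**What the plan says.** The Protocol synopsis defines the primary outcome as baseline-subtracted change "in a clinical measure of stuttering severity (SSI-4), post training (1 week, 6 weeks, and 3 months after training", so three follow-up times are primary. Protocol section 9.1 gives the aim as a mixed design to "compare changes in performance (baseline subtracted) on speech measures between the two groups of participants (tDCS vs. sham".

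The SAP, under Primary outcome measure, enters SSI-4 change scores into a mixed ANOVA. Stimulation group is the between-subjects factor, with "speaking task and time point (1 week, 6 weeks, 12 weeks) as the within subjects factor". Levels are given for time but not for task. After a significant group-by-time interaction, "separate repeated measures ANOVAs will be performed for each stimulation group or with three planned comparisons between groups at each time point". Nothing says which route applies, and no adjustment is stated for the three comparisons.

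For OASES, also conditional on an interaction, the SAP offers one route only: "separate planned comparisons between groups will be performed for each time point".

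The last paragraph of the SAP describes the SSI-4 total as built from three submeasures: frequency, duration and physical concomitants. Under Other pre-specified measures, the SAP applies the primary analysis to the Beck Anxiety Inventory (BAI) and the Premonitory Awareness in Stuttering Scale (PAiS). It gives task levels, reading and conversation, for the % disfluent syllables measured during the training days.

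**The concern.** The trial asks whether tDCS does better than sham. A repeated-measures ANOVA inside one arm cannot answer that. The data are already changes from baseline, so its time effect shows only whether change differs between follow-up visits in that arm. A significant result in the tDCS arm beside a non-significant one in the sham arm is not a comparison of the arms, though it could be reported as one.

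At stake is the information at 1, 6 and 12 weeks. The SAP compares the arms at individual times only if the interaction is significant, and then only if the between-arm route is taken. That choice is left open, and Protocol section 6.3 allows unblinding for analysis once data collection is complete.

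The speaking-task factor is a separate, smaller defect. A single SSI-4 total per visit has no task levels, so the model cannot be fitted as written. BAI and PAiS inherit the same factor by reference.

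**Working it through.** **1. The plan's own figure.** Protocol section 9.2 says that 20 per group "should detect a group difference with an effect size of 0.9 at 80% power" with a 5% false positive rate. Taking this as one two-sided comparison:
- Normal approximation: n = 2(1.960 + 0.842)² / 0.9² = 19.4, so 20 per arm. Power at 20 is Φ(0.9 × √10 − 1.960) = Φ(0.886) = 81.2%.
- Two-sample t-test (noncentral t, 38 df): 79.2%.

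The figure is reproduced. It describes a single between-arm comparison.

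**2. What each test compares** (20 per arm, three times, no task factor):

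| Test | df | Compares tDCS with sham? |
|---|---|---|
| Group effect (change averaged over times) | 1, 38 | Yes |
| Group-by-time interaction | 2, 76 | Yes, profile over time |
| Difference between arms at one time | t, 38 | Yes |
| Time effect within one arm | 2, 38 | No |

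**3. Assumptions for the rest.** Normal change scores with unit SD, equal correlation ρ between times, two-sided 5%. The documents give no correlation, so ρ runs from 0.3 to 0.9.

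**4. Steady benefit of 0.9 at all three times.** The mean of three changes has SD √((1 + 2ρ)/3), which is 0.730 at ρ = 0.3 and 0.966 at ρ = 0.9. The standardised difference is 0.9/0.730 = 1.23 and 0.9/0.966 = 0.93 respectively. Noncentral t gives the group effect 96.7% power at ρ = 0.3 and 81.9% at ρ = 0.9. By simulation, the interaction and the tDCS-arm ANOVA are each significant in about 5% of trials. The tDCS-arm ANOVA is therefore blind to a constant benefit; the group effect is not.

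**5. Type I error** (simulated, no treatment effect):

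| What may count as success | ρ=0.3 | 0.5 | 0.7 | 0.9 |
|---|---|---|---|---|
| Group effect, or interaction plus an unadjusted between-arm time point | 7.8% | 7.0% | 6.2% | 5.6% |
| As above, with the tDCS-arm ANOVA also accepted as follow-up | 8.3% | 7.8% | 7.3% | 6.9% |
| First row, with Holm on the three comparisons | 6.2% | 5.8% | 5.4% | 5.1% |

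Repeat runs differ by 0.1 to 0.2 points, so the second row is best read as about 6.9% to 8.4%. The within-arm option adds 8.3 − 7.8 = 0.5 points at ρ = 0.3 and 6.9 − 5.6 = 1.3 points at ρ = 0.9.

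**6. A fading benefit.** Protocol section 9.2 reports earlier effects of 0.93 at 1 week and 0.50 at 6 weeks. I take these as standardised between-arm differences and assume 0.25 at 12 weeks. The mean is (0.93 + 0.50 + 0.25)/3 = 0.56. Dividing by the SDs in step 4 gives 0.767 and 0.580, with group-effect power of 65.7% and 43.1%. Under the same assumptions, accepting the group effect or an interaction plus a between-arm time point gives about 74% to 82%.

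**7. Speaking task.** Protocol section 6.6 has reading and conversation tasks at each visit, and the SAP defines % disfluent syllables separately for each. For SSI-4 the SAP gives one total from three submeasures, and neither document describes a score for each task. The factor fits % disfluency; it does not fit the SSI-4 total, BAI or PAiS.

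**The case against.** The strongest reply is that the within-arm route opens only after a significant interaction, which itself compares the arms, and that the model tests the group effect in any case. Within-arm ANOVAs are a common way to describe an interaction, and nothing in the SAP says that they decide efficacy. This stands: the route is gated, the added error is small, and the plan does contain between-arm tests. It does not settle the point, because on that route the arms are still not compared at any primary time point.

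Three stronger readings are tempting and are not supported.
- A reader might infer a type I error near 10%, by counting either the group effect or the interaction as success: 1 − 0.95² = 9.75%. The SAP does not say that an interaction alone carries a claim.
- A reader might count it as harm that, with a steady benefit, no time-point comparison is usually triggered. A significant group effect without an interaction is then the correct result. Reporting the time points anyway is better practice, not the repair of a missed effect.
- A reader might conclude that the averaged group effect must be made the deciding test. The text leans that way: for % disfluency the SAP writes "Anticipating a significant effect of group in both measures". It never commits the primary analysis to it, and step 6 of the working shows that the choice has a price.

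It may also be said that reading and conversation are the obvious task levels. They are for % disfluency, but not for an SSI-4 total.

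**Conclusion.** The point holds as a defect of specification that should be fixed. The SAP permits, but does not require, a non-comparative follow-up in place of the comparative one, and it includes a factor that the described SSI-4 total cannot carry. It would be wrong to say that the plan lacks a between-arm test or would miss a steady benefit: the group effect has 82% to 97% power for a constant 0.9.

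The error rates (about 5.6% to 7.8%, or 6.9% to 8.4% with the tDCS-arm ANOVA) apply only if more than one result may count as success. The SAP neither states nor excludes this. They also rest on normal change scores, 20 per arm and assumed correlations. The case for change rests mainly on the wrong contrast and the unreported time-point differences, and less on these rates. The task factor is a wording correction and does not enter the figures.

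**What to change.** Amend the SAP, dated before unblinding:

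1. Replace the either/or follow-up for SSI-4 with between-arm comparisons at each time point. Label any within-arm ANOVA descriptive.
2. Report the tDCS-minus-sham difference in SSI-4 change, with a 95% CI, at 1, 6 and 12 weeks whatever the interaction shows. Borrowing the OASES sentence alone is not enough, because it keeps the interaction condition. If p-values at single times are to carry claims, apply Holm.
3. Remove the speaking-task factor from the SSI-4, BAI and PAiS models. Keep task (reading, conversation) for % disfluency, with its levels stated there.
4. State which between-arm contrast decides the trial. I do not prescribe one. The averaged group effect is strong for a steady benefit, but has only 43% to 66% power for 0.93, 0.50 and an assumed 0.25, so the sponsor should choose deliberately.

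The cost is SAP wording and a little more reporting, with no new data or participants. Adjustment has a price where single time points carry claims: at 0.05/3, the threshold for Holm's first step, t-test power for 0.9 at one time point falls from 79% to 63%.

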6.1. Screening and Eligibility Assessment

When a person who stutters contacts the research team and expresses a desire to participate, they will be sent the PIS outlining the procedures and risks involved in taking part. Screening will take place before volunteers have consented to take part in the study. The screening procedure involves obtaining information in line with tDCS, TMS, and MRI safety guidelines (outlined in the standard operating procedure documents developed within the Medical Sciences Division). Also see exclusion criteria in section 6.3 of this protocol. Screening criteria will be assessed by self-report.

Volunteers will also complete a screening assessment of stuttering severity to ascertain eligibility. In the first instance, one of the named investigators will conduct a screening by videoconference (Skype) to determine severity. Stuttering symptoms are typically increased on the first meeting (when participants are unfamiliar with their conversation partner) and over the telephone/ during videoconferencing. Consequently, if stuttering is determined to be of mild severity at this stage, the volunteer will be informed that they do not meet the inclusionary criteria for the study. If stuttering is of mild-moderate or greater severity, a face-to-face appointment will be scheduled, which will take place on University premises, or at the participant's home or office. The severity of stammering as ascertained on this visit will be used to determine whether participants should be enrolled into the study. If stuttering is of mild-moderate or greater severity, then they will be invited to participate.

Once we have determined eligibility, informed consent will be obtained and a suitable appointment will be scheduled, within three months of the screening. If the participant is deemed ineligible, we will first enquire if they wish to participate in other studies within the lab for which they might be eligible. If they do not, all screening data will be deleted (within a month of notification of ineligibility).

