6.3. Randomisation, blinding and code-breaking

A 'minimisation' sampling procedure will be used, whereby participants' stuttering severity as measured during screening with the SSI-4 will be used to assign successive participants to true stimulation or sham stimulation, minimising group differences in severity. A member of the Departmental of Experimental Psychology who is not involved with the study will be in charge of communicating to the project team what code they should use.

On the basis of this randomisation, half the participants will receive true tDCS stimulation and the other half will be in a control group that will not receive stimulation (sham tDCS). In sham tDCS the current is applied for a sufficiently brief duration to avoid any change in cortical

excitability (up to 30 seconds) but long enough to produce the transitory sensation on the skin associated with real tDCS. Although the stimulation is different, each participant will receive exactly the same speech training throughout the study.

The study will also be double-blinded, meaning that the researchers, study staff, and participants will not know whether the condition involves real or sham tDCS. The stimulator used in the study has a 'study' mode to allow the operator to be blind to the stimulation condition.

The person in charge of the randomisation procedure will have the capacity to unblind the data for analysis once data collection is complete. Data may be unblinded during the data collection only in the context of a serious adverse event potentially related to the type of stimulation or if a patient withdraws from the study and needs to be replaced.

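### The only reading-versus-conversation contrast the SAP spells out for follow-up is within the tDCS arm, so it cannot show whether the tDCS benefit differs by task

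*SAP*

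**What the plan says.** Under Secondary outcome measures, the SAP takes the change in % disfluent syllables for reading and for conversation at 1, 6 and 12 weeks. It then makes three statements that bear on this point.

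- The main analysis is inherited: "Data will be analysed as described above for the primary outcome measure". That model is a mixed ANOVA with stimulation group between subjects and "speaking task and time point (1 week, 6 weeks, 12 weeks) as the within subjects factor".
- Follow-up steps are given for one interaction only: "If a significant interaction between stimulation group and time point is found".
- A further comparison is added. It opens with "Anticipating a significant effect of group in both measures" and plans to "compare the changes in reading with those in conversation at each time point separately for the tDCS group". No matching comparison is given for the sham arm.

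On what the arms share, Protocol 6.3 says that "each participant will receive exactly the same speech training throughout the study", and Protocol 6.6 has reading and conversation recorded at every visit. Protocol 9.2 plans 20 people who stutter per arm.

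**The concern.** Whether tDCS helps one task more than the other is a question about a difference between arms. Within the tDCS arm, the gap between reading change and conversation change mixes two things: any task-specific effect of tDCS, and any task-specific effect of the training, of repetition or of the assessment setting. The sham arm shares the second part. For example, Protocol section 4 and Appendix B combine live and video assessment at baseline and 1 week, but use video alone at the later follow-ups, in both arms. Randomisation removes such influences only when sham is in the comparison.

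The stated premise does not help. Group effects on both tasks can be present and equal in size, and they say nothing about whether the benefit differs by task.

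At stake is a secondary claim. A report could say that tDCS favours one task when the tDCS-minus-sham benefit is the same for both. Conversely, a real task-specific benefit could be hidden by a shared difference in the opposite direction.

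**Working it through.** **1. The plan's own figure.** Protocol 9.2 states that 20 per group detects an effect size of 0.9 with 80% power at 5%. It does not state sidedness; two-sided is assumed.

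- Normal approximation: n per arm = 2 × (1.960 + 0.842)² / 0.9² = 2 × 7.85 / 0.81 = 19.4, rounded up to 20. Power at n = 20 is 81.2%.
- Exact noncentral t (38 df, noncentrality 0.9 × √(20/2) = 2.85): 79.2%.

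The stated figure reproduces, so 20 per arm and two-sided 5% are used below.

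**2. What each contrast estimates.** For each participant let D = reading change minus conversation change at one time point. Let the mean of D be s in sham and s + τ in tDCS. Here s is the task difference shared by both arms and τ is the part specific to tDCS.

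- The tDCS-only comparison tests s + τ = 0.
- The between-arm comparison (group-by-task) tests (s + τ) − s = τ = 0.

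Only the second isolates τ. Masking follows from the same algebra: if s = −0.5 SD and τ = +0.5 SD, the tDCS-arm mean is 0 and the within-arm test has nothing to find.

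**3. Size of the problem when τ = 0.** The documents give neither s nor the SD of D. Shared differences of 0, 0.2, 0.5 and 0.8 SD of D are assumed. The tDCS-only test is a paired t-test with n = 20, 19 df and noncentrality s × √20, that is 0, 0.89, 2.24 and 3.58. The between-arm test is a two-sample t-test on D, 20 against 20, with noncentrality 0 throughout. The per-time-point figures for the tDCS-only test are exact. The others come from 40,000 simulated trials per setting, with an assumed correlation between time points of 0.5 or 0.8.

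| Shared difference (SD) | tDCS-only, one time point | tDCS-only, any of three | Between-arm, one time point | Between-arm, any of three |
|---|---|---|---|---|
| 0 | 5% | 10–13% | about 5% | 10–13% |
| 0.2 | 14% | 23–29% | about 5% | 10–13% |
| 0.5 | 57% | 72–81% | about 5% | 10–13% |
| 0.8 | 92% | 97–99% | about 5% | 10–13% |

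A single group-by-task test averaged over the three time points also stays at about 5%.

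**4. Cost in precision.** The standard error of the within-arm mean of D is SD/√20 = 0.22 SD. For the between-arm difference it is SD × √(2/20) = 0.32 SD. With 80% power, the smallest detectable differences are about 0.66 SD and 0.91 SD.

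**The case against.** **Sham may already be in the model.** A reader might infer from the added comparison that sham plays no part in any test by task. The documents do not support that. The sentence just before it carries over an ANOVA that lists speaking task beside stimulation group. Read literally, that model contains group-by-task and group-by-task-by-time terms. The SAP's exploratory analyses of the training days clearly put group and task in one ANOVA. This part of the objection stands, and it narrows the point. It does not remove it. Neither interaction is named as a test, and follow-up is given only for group-by-time. Reading and conversation are listed as separate secondary outcomes, and the wording about an effect in both measures suggests one ANOVA per task, which would have no group-by-task term. The tDCS-only comparison is also not made conditional on a group-by-task result.

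**No misinterpretation is written down.** A reader might infer that the SAP will credit the within-arm result to tDCS. It states no interpretation. Whether treated participants changed more in one task than in the other is a legitimate descriptive question, and the paired test is valid for it. The risk is one of misreading.

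**Familiarity is not shown to act on conversation alone.** The protocol's screening section says "Stuttering symptoms are typically increased on the first meeting (when participants are unfamiliar with their conversation partner", and the sentence goes on to telephone and video contact. It is tempting to read this as the protocol saying that conversation will improve with familiarity while reading will not. The passage speaks of symptoms generally, and baseline follows a video screening and a face-to-face screening, by which time some of any first-meeting excess may have passed. A shared task difference is possible; the documents do not establish one.

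**The percentages have no anchor.** This is true: the shared differences are assumptions, which is why the range starts at zero. If group effects in both tasks are a condition for running the comparison, the unconditional rates are lower. At an assumed group effect of 0.5 SD, power with 20 per arm is only about one third per task.

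**Conclusion.** The point holds in a limited form. The one task contrast the SAP spells out for follow-up cannot tell a tDCS-specific task effect from one shared with sham, and the contrast that could do so is at most implicit in an ambiguously described ANOVA. That conclusion rests on the design and needs no assumed figures.

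The size does rest on assumptions: normally distributed differences, equal SDs in the two arms, 20 complete participants per arm, and the comparison always being run. Under these, the chance of a significant within-tDCS result with no tDCS-specific task effect runs from 5% (no shared difference) to 92% (0.8 SD) at a given time point.

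The primary outcome and the overall benefit of tDCS are still judged between arms and are not affected. What is exposed is any statement that tDCS helps reading more than conversation, or the reverse.

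**What to change.** Amend the paragraph on % disfluent syllables in the SAP to do three things.

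1. State that the ANOVA is joint over reading and conversation, with group between subjects and task and time point within subjects.
2. Name group-by-task as the test of a task-specific tDCS benefit: tDCS against sham on each participant's reading-minus-conversation change, at 1, 6 and 12 weeks.
3. Report the within-tDCS contrast as description only, beside the same contrast in sham.

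The SAP provides for nonparametric methods when data are not normal. In that case the same per-participant difference can be compared between arms with a rank-based test, so the change still works.

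The cost is a few lines of SAP text; no new data are needed. The downside is precision: with 20 per arm and 80% power, the between-arm contrast detects about 0.91 SD, against about 0.66 SD within the arm. That loss is acceptable because the more sensitive test answers a different question. A non-significant group-by-task result should therefore not be read as showing equal benefit in the two tasks.
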